#### **3 OBJECTIVES OF THE STUDY**

#### Phase 1 Objectives

#### 3.1.1 Primary

- To define the MTD and the RP2D for orally administered VK-2019 monotherapy in patients with recurrent or metastatic NPC.
- To evaluate and characterize the safety profile of single agent VK-2019 in adult patients with recurrent or metastatic NPC.

#### 3.1.2 Secondary

- To evaluate the anti-tumor activity of single agent VK-2019 per RECIST v1.1.
- To characterize the single-dose and steady state pharmacokinetic profile of single agent VK-2019 in adult patients with recurrent or metastatic NPC.
- To evaluate the anti-EBV activity by reduction of plasma EBV-DNA of single agent VK-2019 in adult patients with recurrent or metastatic NPC.

#### 3.1.3 Exploratory

- To explore blood PD markers.
- To explore PD markers such as alteration in EBV specific gene expression, both lytic and latent EBV genes.
- To explore exposure-response relationships between VK-2019 exposure and the PD endpoints (safety, efficacy, and laboratory correlatives).

#### Phase 2a Objectives

#### 3.2.1 Primary

- Evaluate preliminary efficacy (ORR, DOR, DCR, PFS, survival rate, and OS) of orally administered VK-2019 monotherapy in adult patients with recurrent or metastatic NPC.
- Confirm the safety and tolerability of orally administered VK 2019 monotherapy in adult patients with recurrent or metastatic NPC.

#### 3.2.2 Secondary

- To further characterize select PK parameters associated with orally administered VK-2019 monotherapy in adult patients with recurrent or metastatic NPC.
- Evaluate the anti-EBV activity by reduction of plasma EBV-DNA of orally administered VK-2019 monotherapy in adult patients with recurrent or metastatic NPC.

#### 3.2.3 Exploratory

- To explore both blood and intratumoral PD markers.
- To explore PD markers such as alteration in EBV specific gene expression, both lytic and latent EBV genes.
- To explore exposure-response relationships between VK-2019 exposure and the PD endpoints (safety, efficacy, and laboratory correlatives).

[figure not shown]
## 4 STUDY DESIGN

This is a phase 1/2a, open-label, multicenter, multi-dose, dose-escalation trial of VK-2019, a potent and selective inhibitor of the EBV latency program through its specific binding to a viral target, EBNA1.

For each patient enrolled, the study will consist of at least three periods: Screening (up to 28 days), Treatment (comprised of 28-day dosing cycles), and Follow up (comprised of a safety follow-up and long-term follow-up for survival status).

This trial is divided into three parts (Figure 1): Phase 1 Dose Escalation, Phase 1 Dose Expansion, and Phase 2a Dose Expansion. One sub-study, collecting tumor biopsies, will be conducted during the Phase 2 Expansion part of the trial.

#### Figure 1: Study Design Schema

Note: Three Phase 1 and two Phase 2 dose expansions are not specifically planned. The total number of expansions opened will depend upon biological and clinical activity observed in the trial

#### **Phase 1 Dose Escalation**

Dose escalation in this trial will be conducted utilizing both an accelerated titration, based in part upon a 3B design proposed by Simon et al (21), coupled with a "rolling six" design (22). Five dose escalation cohorts are planned, but additional dose escalation or intermediate de-escalation cohorts may be explored based upon emerging safety and/or PK data.

By utilizing these designs it is expected to maximize accrual at pharmacologically relevant doses, both by potentially minimizing accrual at subtherapeutic dose levels and more efficiently establishing an understanding of the safety profile of VK-2019 (23).

Dose escalation will initially proceed according to the accelerated titration design, enrolling one new patient per dose level. Upon any instance of a VK-2019 related Grade  $\geq$  2 AE during Cycle 1, dose escalation will convert to the Rolling Six design in which 3-6 patients per dose level will be enrolled.

See Section 6.2 for dose escalation procedures.

### Phase 1 Dose Expansion

During dose escalation, one or more cohorts may be selected for expansion, enrolling up to 16 patients (inclusive of the patients already enrolled at the same dose during escalation) at any dose level that is assessed to either be the MTD or have sufficient activity to meet criteria as a BCAD. See Section 6.7 for details on initiating a Phase 1 Dose Expansion.

#### Phase 2a Dose Expansion

Further dose expansion in the Phase 2a part of the trial may be explored by utilizing the Simon 2 Stage design. Up to an additional nine patients may be enrolled at a particular dose if two or more objective responses (at least one must be confirmed) are observed out of 16 patients at that dose in the Phase 1 part of the trial (for a total accrual of up to 25 patients).

See Section 6 for details on initiating a Phase 2a Dose Expansion.

## 5 ELIGIBILITY CRITERIA

The inclusion and exclusion criteria for this study are provided on the Eligibility Checklist below.

A patient must meet all of the inclusion criteria and must not meet any of the exclusion criteria to be eligible to participate in this study.

The checklist may be utilized to review and confirm each patient's eligibility prior to registration (unless a separate checklist is required by the institution). If used for confirmation of eligibility, the completed, signed, and dated checklist will be retained in the patient's study file and the study's regulatory binder.

# Patient Eligibility Checklist

I. Protocol Information					
	Protocol Title:	Phase 1-2a open-label, multicenter clinical trial of a novel small molecule EBNA1 inhibitor, VK-2019, in patients with Epstein-Barr Virus positive nasopharyngeal cancer, with pharmacokinetic and pharmacodynamic correlative studies			
	Protocol number (Sponsor/Institution):	VK-2019-001/			
	Principal Investigator:				

### **II.** Patient Information

Patient Identifier (i.e., Subject Number, etc.):			
Gender	Male	Female	

### **III.** Study Information

### **Inclusion** Criteria

	Prospective Study Patient Must MATCH ALL these Inclusion Criteria to be Eligible	Yes	No	Supporting Documentation *
1.	Informed consent obtained prior to any protocol mandated assessment			
2.	Age $\geq 18$			
3.	Either loco-regionally recurrent or metastatic EBV-positive nasopharyngeal carcinoma not amenable to curative treatment. EBV positivity is defined as high EBV viral load in plasma (> 4000 genomes per $\mu$ g plasma DNA) and/or biopsy tissue positive for EBV			
4.	Prior palliative radiation must have been completed at least 2 weeks prior to study Cycle 1 – Day 0			
5.	Prior anti-cancer systemic treatment must have been completed greater than 4 weeks prior to the first dose of VK-2019			

	Prospective Study Patient Must MATCH ALL these Inclusion Criteria to be Eligible	Yes	No	Supporting Documentation *
6.	Toxicities related to prior anti-cancer therapy must have returned to Grade 1 or less. Peripheral neuropathy must be Grade 2 or less. Chronic but stable toxicities Grade > 1 (e.g., dysphasia, G tube dependence, etc.) may be allowed after agreement between the Investigator and Sponsor.			
7.	For the dose expansion phase in Phase 1 and Phase 2a: Patients must have RECIST v1.1 measurable disease, defined as at least one lesion that can be accurately measured in at least one dimension (longest diameter to be recorded for non-nodal lesions and short axis for nodal lesions) as $\geq 10$ mM with spiral CT scan, MRI, or calipers by clinical exam			
8.	ECOG performance status score of $\leq 2$ at study entry.			
9.	Absolute neutrophil count > 1500/µL (stable off any growth factor for at least 1 week of study drug administration)			
10	Hemoglobin > 9g/dL (transfusion to achieve this level is permitted )			
11.	Platelet count > 75 x 103/ $\mu$ L (transfusion to achieve this level is NOT permitted )			
12.	Serum aspartate transaminase (AST) and serum alanine transaminase (ALT) ≤ 2.5 x upper limit of normal (ULN)			
13	Total serum bilirubin $\leq 1.5 \text{ x ULN}$			
14	Serum creatinine $\leq 1.5$ x ULN or creatinine clearance $\geq 50$ mL/min as calculated per Cockcroft-Gault equation			
15	Urinary protein < 2+ by dipstick. If dipstick $\ge$ 2+, then a 24-hour urine collection can be done and the patient may enter only if urinary protein is < 1 g/24 hour			

		г	
Prospective Study Patient Must MATCH ALL these Inclusion Criteria to be Eligible	Yes	No	Supporting Documentation *
16. Sexually active patients must agree to utilize birth control method during treatment and for 18 weeks after the last dose of VK-2019. Using effective birth control methods as defined in https://www.cdc.gov/reproductivehealth/unintended pregnancy/pdf/contraceptive_methods_508.pdf . See Appendix 3 and Section 17.3			
17. Willingness and ability to comply with the study scheduled visits, treatment plans, laboratory tests and other procedures			
Exclusion Criteria		· · · · ·	
Prospective Study Patient Must NOT Match ANY of These Exclusion Criteria	Yes	No	Supporting Documentation *
1. Severe or active symptomatic cardiopulmonary diseases, including unstable angina, congestive heart failure, or peripheral vascular disease within 12 months prior to study drug administration; and/or chronic obstructive pulmonary disease exacerbation or other respiratory illness requiring hospitalization within 4 weeks prior to study drug administration. Patients with effectively treated conditions (eg, stenting for coronary artery disease) are eligible if stable for at least 4 weeks prior to study drug administration.			
2. Metastatic disease with active central nervous system (CNS) involvement, defined as parenchymal brain involvement. Patients with cranial nerve or base of skull involvement without the above are eligible. Patients with CNS metastases that are stable on imaging at least 1 month following focal treatment with radiation are eligible			
3. Concurrent treatment with systemic cancer directed therapy including complementary, alternative, herbal or nutritional supplement-based treatments whose purpose is for anti-cancer effect			

		1	
Prospective Study Patient Must NOT Match ANY of These Exclusion Criteria	Yes	No	Supporting Documentation *

 
Known history of human immunodeficiency virus (HIV) unless the HIV-positive patients has:
 
			
• A stable regimen of highly active anti-retroviral therapy (HAART)			
• No requirement for concurrent antibiotics or antifungal agents for the prevention of opportunistic infections			

 
A CD4 count above 250 cells/mcL and an undetectable HIV viral load on standard PCR-based test
 
			
5. Serious uncontrolled medical disorder or active infection which would, in the opinion of the Investigator, impair the ability of the subject to receive protocol therapy or whose control may be jeopardized by the complications of this therapy			

 
Currently taking drugs that inhibit or induce OATP1B1 or OATP1B3 within 5 half-lives of that agent. Examples are included in Appendix 2.
 
			
7. Have received a prior organ allograft or allogeneic bone marrow transplant.			
8. Current non-prescription drug or alcohol dependence			
9. For all female patients, pregnancy or breastfeeding			
10. All female patients with reproductive potential must have a negative pregnancy test (serum or urine) prior to enrollment			
11. Other severe acute or chronic medical or psychiatric condition or laboratory abnormality that may increase the risk associated with study participation or study drug administration, or may interfere with the interpretation of study results, or in the judgment of the investigator would make the patient inappropriate for entry into the study			

Prospective Study Patient Must NOT Match ANY of These Exclusion Criteria	Yes	No	Supporting Documentation *

12. Corrected QT by Fridericia's formula (QTcF) of > 470 ms average (mean) on triplicate ECG performed during screening

			

\* All patient files must include supporting documentation to confirm eligibility. The method of confirmation can include, but is not limited to, laboratory test results, radiology test results, subject self-report, and medical record review.

#### V. Statement of Eligibility

By signing this form of this study, I verify that this subject is:  $\Box$  eligible /  $\Box$  ineligible for participation in the study.

Study Coordinator Printed Name:	Date:
Signature:	
Investigator Printed Name:	Date:
Signature:	
Additional Reviewer Printed Name (if required):	Date:
Signature:	

#### Age and Reproductive Status

Sexually active patients (excluding women who are not of childbearing potential) must use effective methods of birth control during treatment and for up to 18 weeks after the last dose of VK-2019. See Appendix 3.

Acceptable methods of highly effective birth control include:

- Condom with spermicide
- Diaphragm and spermicide
- Cervical cap and spermicide
- Hormonal implant
- Intrauterine device
- Male or female surgical sterilization
- Oral contraceptive pills

Women must not be breastfeeding.

Women of child-bearing potential (WOCBP) include any female who has experienced menarche and who has not undergone successful surgical sterilization (hysterectomy, bilateral tubal ligation, or bilateral oophorectomy), and who is not postmenopausal.

## 6 STUDY TREATMENT AND CONDUCT

## Safety Review Committee

During the Dose Escalation and Dose Expansion parts of this study, an SRC will review safety, tolerability, PK, and, if available, PD data for the purposes of oversight and decision making.

The SRC's membership will consist of:

- Two external, independent oncologists (one of which will serve as SRC Co-Chair)
- The Protocol Chairperson (who will also serve as SRC Co-Chair)
- The sponsor Medical Monitor and/or Chief Medical Officer
- Principal Investigators from each site

Additional attendees including (but not limited to) the study statistician, pharmacologist, pharmacovigilance representatives, site staff, or sponsor representatives may be invited to participate on an ad hoc basis.

More information about SRC membership and roles and responsibilities is contained in the SRC Charter.

#### 6.1.1 During Phase 1 Dose Escalation

After completion of a dose escalation cohort, the SRC will convene to evaluate the safety, tolerability, PK, and, if available, PD data of VK-2019 from that cohort with the purpose of deciding upon the next dose level.

Upon reviewing data from that cohort, the SRC may decide to:

- Escalate to the next dose level
- Convert to the rolling-six dose escalation schema
- Enroll up to a maximum of 6 evaluable patients
- De-escalate to either a previously explored lower dose level (up to a maximum of 6 evaluable patients) or to an intermediate lower dose level
- Discontinue dose escalation in the trial
- Initiate a Phase 1 Dose Expansion Cohort
- Consider alternative dosing frequencies or intermittent dosing schedules
- Terminate the trial
- Defer their decision until additional data from patients in that cohort and/or other cohorts becomes available

Additionally, PK profiles for patients treated two dose levels below a dose level under consideration for escalation will be required by the SRC prior to starting a given dose level, e.g., Cohort 3 will begin only after PK information on Cohort 1 is available for review. If super-proportional PK is observed following the single-dose PK on C1D0, the dose of VK-2019 may be modified to account for the increase in exposure. If significantly less than dose proportional exposure is observed, dose escalation may be stopped and one of the doses with the highest exposure may be selected for expansion.

Any patient started on treatment in error, i.e., he/she failed to comply with all of the selection criteria, but still meets the criteria of an evaluable patient will be reviewed on a case by case basis by the SRC to determine if the patient should be included or excluded in the decision for dose escalation.

During the dose escalation, decisions made by the SRC will be documented and provided to the investigators prior to dosing any new patients.

## 6.1.2 During Phase 1 Dose Expansion

Upon completion of any Phase 1 Dose Expansion Cohort in the trial, the SRC will convene to review accumulating safety, tolerability, pharmacokinetics, and, if available, pharmacodynamic data. Additionally, SRC reviews will be required at various intervals during a given expansion cohort. The timing and criteria for convening these reviews are described in the SRC Charter.

Upon review of this data, the SRC may decide to:

- Continue the trial as planned
- Stop enrollment into a particular expansion cohort or all cohorts in the Phase 1 Dose Expansion part of the trial
- De-escalate one or more of the doses being explored in the expansion
- Initiate a Phase 2a Dose Expansion Cohort
- Consider alternative dosing frequencies or intermittent dosing schedules
- Terminate the trial
- Defer their decision until additional data becomes available
- 6.1.3 During Phase 2a Dose Expansion

Upon completion of any Phase 2a Dose Expansion Cohort in the trial, the SRC will convene to review accumulating safety, tolerability, pharmacokinetics, and, if available, pharmacodynamic data. Additionally, SRC reviews will be required at various intervals during a given expansion cohort. The timing and criteria for convening these reviews are described in the SRC Charter.

Upon review of this data, the SRC may decide to:

- Continue the trial as planned
- Stop enrollment into a particular expansion cohort or all cohorts in the Phase 2a Dose Expansion part of the trial
- De-escalate one or more of the doses being explored in the expansions
- Consider alternative dosing frequencies or intermittent dosing schedules
- Terminate the trial
- Defer their decision until additional data becomes available

## **Dose Escalation Procedures**

The starting dose for VK-2019 is 60 mg QD. Sample dose escalation tables are below in Table 7, detailing a sample dose escalation schema based upon when escalation converts from Accelerated Titration to a Rolling Six design.

6.2.1 Definition of a Completed Cohort and an Evaluable Patient Each dose escalation cohort will consist of either:

- 1 evaluable patient (Accelerated Titration cohorts), or
- 3-6 evaluable patients (Rolling Six cohorts)

[figure not shown]
To be considered evaluable, a patient will have and one of the following:

- Received 75% of doses during Cycle 1, or,
- Received at least one dose of VK-2019 and experienced a DLT during Cycle 1
- 6.2.2 Dose Escalation in Accelerated Titration Cohorts

Upon completion of an accelerated titration cohort (Figure 2),

- IF: No VK-2019 related Grade ≥ 2 AEs occur during Cycle 1; THEN: Dose escalation may proceed to the next accelerated titration cohort (no greater than a 100% dose increase).
- IF: The patient experiences any VK-2019 related Grade ≥ 2 AE during Cycle 1 (not meeting the definition of a DLT); THEN: Convert the current cohort to the Rolling Six design and enroll an additional 2-5 patients (3-6 total).
- IF: The patient experiences a DLT; THEN: Convert to the Rolling Six design and enroll an additional five patients (six total).

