#### **Figure 2: Accelerated Titration Dose Escalation Schema**

6.2.3 Dose Escalation in Rolling Six Cohorts

Upon completion of a Rolling Six cohort (a minimum of three, maximum of six evaluable patients), if:

• 0 of 3 patients experience a DLT; dose escalation may proceed to the next cohort (no greater than a 50% dose increase)

- 1 of 3 patients experience a DLT; an additional three evaluable patients will be enrolled into the cohort
- $\leq 1$  of 6 patients experience a DLT; dose escalation may proceed to the next cohort (no greater than a 50% dose increase)
- ≥ 2 patients experience a DLT; the MTD has been exceeded and further enrollment into that cohort will cease. Lower-dose cohorts may then be explored until the MTD has been determined, including intermediate doses.

Dose Escalation Schema	Target Dose / Actual Dose	Dose Increase
	60 mg / 60 mg	n/a
All asharts annalled using Assalanted	120 mg / 120 mg	100%
All cohorts enrolled using Accelerated Titration	240 mg / 230 mg	100%
Thaton	460 mg / 460 mg	100%
	920 mg / 920 mg	100%
	60 mg / 60 mg	n/a
Delling six equalles at the sing of the	90 mg / 90 mg	50%
Rolling-six enrollment begins at the 60 mg cohort	135 mg / 120 mg	50%
oo mg conort	180 mg / 180 mg	50%
	270 mg / 260 mg	50%
	60 mg / 60 mg	n/a
Dolling giv angultment begins at the	120 mg / 120 mg	100%
Rolling-six enrollment begins at the 120 mg cohort	180 mg / 180 mg	50%
120 mg conort	270 mg / 260 mg	50%
	390 mg / 380 mg	50%
	60 mg / 60 mg	n/a
Dalling six annullment begins at the	120 mg / 120 mg	100%
Rolling-six enrollment begins at the 230 mg cohort	240 mg / 230 mg	100%
230 mg conort	345 mg / 320 mg	50%
	480 mg / 460 mg	50%
	60 mg / 60 mg	n/a
Dalling six annullment begins at the	120 mg / 120 mg	100%
Rolling-six enrollment begins at the 460 mg cohort	240 mg / 230 mg	100%
	460 mg / 460 mg	100%
	690 mg / 690 mg	50%

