## **Dose-limiting Toxicity**

DLTs will be determined based on the incidence and intensity of AEs assessed as being at least possibly related to VK-2019 and occurring up to 28 days after initiation of QD VK-2019 dosing on C1D0.

- 6.3.1 Dose-limiting Hematologic Toxicity
  - Grade 4 neutropenia > 7 days
  - Grade 4 thrombocytopenia or Grade 3 thrombocytopenia associated with bleeding or requiring platelet transfusion
  - Grade 3 febrile neutropenia
  - Grade 4 anemia or anemia that requires blood transfusion
- 6.3.2 Dose-limiting Non-hematologic Toxicities

- Any Grade 3 or higher non-hematology toxicity, excluding the following:
  - Toxicities assessed by Investigator as clearly related only to disease progression or intercurrent illness
  - Elevations of AST, ALT, and bilirubin, that correct to Grade 1 within one week and do not meet any of the definitions of acute liver injury as listed below
  - o Other asymptomatic laboratory abnormalities
  - Grade 3 fever without neutropenia that returns to Grade 1 or less within 3 days, and is not associated with hemodynamic compromise (including hypotension, or clinical or laboratory evidence of end organ perfusion impairment)
  - Grade 3 diarrhea, nausea, vomiting, or abdominal pain that returns to Grade 1 or baseline within 3 days and with medical intervention
  - Grade 3 pruritis or rash that returns to Grade 1 or baseline within 7 days or baseline with medical intervention
  - o Grade 3 fatigue
  - Grade 3 tumor flare (defined as pain, irritation or rash that localizes to sites of known or suspected tumor)

A DLT will also include:

- A laboratory finding of acute liver injury defined as:
  - Sustained (> 1 week) doubling of AST or ALT levels to no less than 4 x ULN, or sign of increasing functional liver impairment with > 2x baseline increase in total bilirubin
  - o Increased AST or ALT levels above 8xULN
  - Suspected acute liver injury (per Hy's law) ALT/AST > 3 x ULN in combination with Total Bilirubin > 2 x ULN in the absence of cholestatic injury (ALP < 2 x ULN) and no other cause identified.

- Any AE resulting in a patient missing < 7 days of dosing with VK-2019
- Any AE not otherwise meeting the criteria or timing of a DLT as defined above, but is declared a DLT by the SRC

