#### **Definition of the MTD**

The MTD is defined as the highest dose level of VK-2019 at which fewer than two DLTs are observed in six evaluable dose escalation patients at that dose level.

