# 9 PATIENT MONITORING, TOXICITY MANAGEMENT, AND DOSE MODIFICATIONS

Each patient will be assessed for the development of any toxicity as outlined in Section 13. Dose adjustments will be made according to the system showing the greatest degree of toxicity. The table below outlines parameters for dose holds, dose reductions, resuming dosing, and study drug discontinuance for AEs assessed to be at least possibly related to VK-2019.

Adverse Event	Action with VK-2019 and Toxicity Management
All Grade 1 AEs	Continue VK-2019 at the same dose level. Manage with supportive therapy at the Investigator's judgment.
All Grade 2 AEs	Continue VK-2019 at the same dose level. Manage with supportive therapy at the Investigator's judgment.
All Grade $\geq$ 3 AEs (unless otherwise noted below)	Hold VK-2019 and administer supportive therapy as required in accordance with local practice/guidelines.
	If AE resolves to Grade $\leq 2$ within 21 days, VK-2019 may be restarted at the same dose (unless meeting criteria for a DLT) or a lower dose pending discussion between the investigator and Sponsor.
	If AE does not resolve to Grade $\leq 2$ after 21 days, permanently discontinue VK-2019 and observe the patient until the AE is resolved.
Grade ≥ 2 diarrhea	Manage with Loperamide (4mg at first onset, followed by 2mg every 2-4 hours (or with each loose bowel movement) until diarrhea free for 12 hours (maximum daily dose: 16 mg/24 hours). If loperamide is ineffective, consider adding Lomotil (5 mg, four times a day), or tincture of opium (15- 20 drops orally every 4 hours), or octreotide (150 to 300 mcg SQ twice daily). Modifications to this regimen can be made per local standard practice.
	Hold VK-2019 and manage as above until resolves to Grade $\leq 2$ .
Grade $\geq$ 3 diarrhea	If diarrhea resolves to Grade $\leq 2$ within 21 days, VK-2019 may be restarted at the same dose (unless meeting criteria for a DLT) or a lower dose pending discussion between the investigator and Sponsor.
	If diarrhea does not resolve to Grade $\leq 2$ after 21 days, permanently discontinue VK-2019 and observe the patient until the AE is resolved.

Adverse Event	Action with VK-2019 and Toxicity Management
Nausea/vomiting, all grades	Standard antiemetics for the treatment of nausea and/or vomiting may be used. If it has been demonstrated that there is significant emetogenic potential based on individual and cumulative AE data, prophylactic anti-emetics may be used using ASCO guidelines.

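### DLT evaluability counts 75% of Cycle 1 doses without tying them to the assigned dose level, so a patient reduced after a non-DLT Grade ≥ 3 event can count as DLT-free at the original dose

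*Protocol*

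**What the plan says.** **Evaluability.** Protocol 6.2.1, the synopsis and SAP 2.2.1 give two routes. The first is "Received 75% of doses during Cycle 1, or". The second is "Received at least one dose of VK-2019 and experienced a DLT during Cycle 1". The first is a count of doses. None of the three places names the dose level or mentions reductions.

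**Use of the count.** In Protocol 6.2.3, "0 of 3 patients experience a DLT; dose escalation may proceed to the next cohort"; at most one DLT in six also permits escalation. The MTD is the highest dose at which "fewer than two DLTs are observed in six evaluable dose escalation patients at that dose level". The synopsis version of the MTD definition refers to patients treated at that dose.

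**Dose reduction.** Protocol Section 9 continues Grade 1 and Grade 2 events at the same dose. For related Grade ≥ 3 events it requires a hold. If the event settles to Grade 2 or less within 21 days, "VK-2019 may be restarted at the same dose (unless meeting criteria for a DLT) or a lower dose", after discussion between investigator and sponsor. If the same event recurs, restart is one level lower. Neither row excludes Cycle 1.

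**DLT list.** Protocol 6.3.2 makes Grade ≥ 3 non-hematologic toxicity a DLT, with exclusions that include "Grade 3 fatigue", Grade 3 tumor flare, and gastrointestinal events that recover within three days. Under 6.3.1, Grade 3 neutropenia, and Grade 3 thrombocytopenia without bleeding or transfusion, are also not DLTs. Dose reduction is not a criterion. Missed dosing because of an AE is a criterion, but the synopsis sets it at more than 7 days and Protocol 6.3.2 at fewer than 7 days.

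**The concern.** The 75% requirement is there so that a patient called DLT-free has had enough exposure to the dose being judged. As worded, it secures a number of doses and not exposure at that dose. It can fail for exactly the patients in whom the assigned dose was lowered because of toxicity.

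Upward changes are dealt with: Protocol 6.2.4 and 6.2.5 (and SAP 2.2.4 and 2.2.5) exclude an escalated patient from DLT assessment at the new dose. Downward changes are not mentioned. The MTD is a Phase 1 primary objective, and reaching it is one of the two grounds for opening a Phase 1 expansion cohort. A denominator that includes patients barely exposed to the dose makes that dose look better tolerated than the evidence supports.

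**Working it through.** **Plan's own figures.** The documents state no operating characteristics for the DLT or MTD rule. The only ones given are for the Simon design. They reproduce (type I error 0.095, power 0.903, early stopping 0.515) but do not bear on this point.

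**Who is affected.**
- Toxicity that is a DLT: the patient is evaluable by the second route and counts against the dose. Not affected.
- Grade 1 or 2 event: Section 9 gives no reduction. Not affected.
- Related Grade ≥ 3 event that is not a DLT, followed by a Cycle 1 reduction, with at least 21 doses taken in all: counted as DLT-free at the original dose. Affected.

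**How little exposure can qualify.** Once-daily dosing over a 28-day cycle gives 28 planned doses, and 0.75 × 28 = 21. Take an extreme case: one dose at the assigned level, 7 missed after Grade 3 fatigue, 20 at the next lower level. Doses taken are 1 + 20 = 21, so the patient is evaluable with 1/28 = 3.6% of planned doses at the assigned level. Using sample dose levels from Protocol Table 7:
- 230 to 120 mg: (1 × 230 + 20 × 120) / (28 × 230) = 2,630 / 6,440 = 41% of planned dose
- 460 to 230 mg: 5,060 / 12,880 = 39%
- 690 to 460 mg: 9,890 / 19,320 = 51%

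A later event is less extreme. With 14 full doses, 7 missed and 7 reduced, 230 to 120 mg gives 4,060 / 6,440 = 63%.

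**Missed-dose criterion.** Under the synopsis (more than 7 days), an AE hold of up to 7 missed days is not a DLT by this criterion. Under 6.3.2 as printed (fewer than 7 days), a hold of 1 to 6 missed days is itself a DLT, which leaves only exactly 7 missed doses or a hold that costs none. The case above qualifies under both, but under 6.3.2 it is nearly the only kind that does.

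**A cohort.** Six patients with one DLT and two such reductions read as 1/6, and escalation may proceed. Without the two, the result is 1/4 and two more evaluable patients are needed. The chance that they add at least one DLT is 1 − (1 − p)²: 0.36 at an assumed p of 0.20 and 0.55 at 0.33.

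**Effect on the six-patient rule.** Let d be the DLT rate as now counted and q the rate of Cycle 1 reductions for non-DLT events. Both are assumptions; 17% is chosen as just under the Phase 1 hypothesis of less than 18%. As written, P(≤ 1 in 6) = (1 − d)⁶ + 6d(1 − d)⁵, whatever q is. If every reduced patient is replaced, the rate becomes d / (1 − q).

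| d | As written | q = 5% | q = 10% | q = 20% | q = 30% |
|---|---|---|---|---|---|
| 10% | 0.886 | 0.875 | 0.863 | 0.833 | 0.793 |
| 17% | 0.729 | 0.707 | 0.683 | 0.625 | 0.551 |

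This slightly overstates the change, because a patient reduced late, with 21 doses already taken at the assigned level, would stay evaluable.

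**The case against.** The strongest reply is that the gap is narrow and watched. Most Grade ≥ 3 non-hematologic events are DLTs. Reduction after a first event is optional and involves the sponsor. Any related Grade ≥ 2 event in Cycle 1 ends single-patient titration. The Safety Review Committee (SRC) reviews each completed cohort, may defer or de-escalate, and may declare any AE a DLT. The RP2D definition weighs cumulative toxicity. Protocol 14.5.1 tabulates events leading to dose modification by dose level.

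Much of this stands as a limit on size. It does not close the gap. Conversion to Rolling Six keeps the index patient, so one reduced patient and two DLT-free patients still read as 0/3. The SRC's powers are discretionary, and Protocol 6.1.1 provides case-by-case review of inclusion only for patients started in error. SAP 7.14.1 narrows the AE summaries to events leading to treatment discontinuation or death, plus DLTs, and SAP 7.9 gives dose intensity but not Cycle 1 reductions.

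A second reply is that making reduced patients non-evaluable takes their toxicity out of the count altogether. That is fair, and it is why the reductions need to be shown beside the DLT counts.

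A reader might infer that any patient reduced for toxicity is counted as tolerating the dose, or that the MTD will be set too high. The documents support neither. The text is silent on dose level; it does not say that doses at any level count. Patients with a DLT count against the dose, and escalation is a permitted step after SRC review, not an automatic one.

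**Conclusion.** The point holds for one group: patients reduced in Cycle 1 after a related Grade ≥ 3 event that is not a DLT. For them the stated rule allows DLT-free status at a dose they may hardly have taken, and the bias runs towards tolerability.

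Its size cannot be derived from the documents, because no reduction rate is given. At assumed reduction rates of 5% to 10%, replacement lowers the chance of passing the six-patient rule by about 1 to 5 percentage points (0.886 to 0.875–0.863 at a 10% DLT rate; 0.729 to 0.707–0.683 at 17%). At 30% the fall is about 9 points (0.886 to 0.793) and 18 points (0.729 to 0.551). The width of the gap also depends on the unreconciled missed-dose criterion. The 3.6% and 41% figures show what the rule permits, not what is typical. This is a definition that should be fixed; it is not evidence that a particular MTD is wrong.

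**What to change.** 1. In the synopsis, Protocol 6.2.1 and SAP 2.2.1, define the first route as at least 75% of planned Cycle 1 doses (21 of 28) received at the assigned dose level. Keep the second route (any dose plus a DLT) unchanged.
2. Report Cycle 1 dose reductions for related AEs by cohort, beside the DLT counts given to the SRC and in the SAP tables.
3. Reconcile the missed-dose DLT criterion between the synopsis and Protocol 6.3.2. Which version applies, and whether a Cycle 1 reduction should itself count as a DLT, are decisions for the sponsor.

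The cost is one sentence in each of three places and one added table column. An occasional cohort will need a replacement patient to reach its existing evaluable number. The SAP serves an abbreviated study report. If escalation is already complete, the workable step is to list, by cohort, the patients counted as evaluable who had a Cycle 1 reduction, so that a reader can see whether any MTD statement depends on them.
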